5.1.1 Survey Conduct

An electronic consent and survey questionnaire approved by an Institutional Review Board (IRB) will be used by RTI to program the online survey for the purpose of standardizing responses among patients.

Each patient will complete up to 7 web-based surveys over the duration of the study. Each survey is anticipated to take no more than 20 minutes on average.

All assessments, except mortality, will be patient-reported; medical records will not routinely be requested or reviewed as part of this observational study unless required for safety reporting purposes. As patient recall over time may be limited, partial responses as in the case of dates of onset, and/or estimates of numerical information will be accepted.

Participation in the study is contingent on continued use of XERMELO. Each survey will establish ongoing treatment with XERMELO and continued consent to study participation prior to subsequent data collection.

The initial survey is intended to gather Baseline information, which may include:

- Sociodemographics (age, year of birth, sex, race, ethnicity, education, geographic region)
- Current medical history as it relates to CS, NET burden, NET location, and related conditions
 - Location of NET
 - Date of diagnosis; CS and NET
 - CS-related hospitalization(s)
 - CS-related ER visit(s)
 - NET-related surgery (eg, tumor debulking, lysis of adhesions)
- Satisfaction with CS, CS-related diarrhea and/or flushing control prior to starting XERMELO, where applicable
- Height and weight
- Concomitant medication as it relates to the following:
 - Long-acting SSA therapy

- Use of rescue medication - short-acting SSA
- Systemic tumor-directed therapy
- Liver-directed therapy (eg, chemoembolization)
- WPAI-SHP

The initial survey should be completed no later than 30 days, and subsequent surveys should be completed no later than 14 days, after the unique survey link has been provided to the patient via e-mail. Patients will be asked to complete a survey every 6 months for up to 3 years. The following patient-reported data may be collected as described in [Appendix A](#):

- Satisfaction with CS, CS-related diarrhea and/or flushing control after initiating XERMELO, where applicable
- PGIC
- Concomitant medication as it relates to the following:
 - Change in use of rescue medication - short-acting SSA
 - Change in long-acting SSA therapy
 - Systemic tumor-directed therapy
 - Liver-directed therapy (eg, chemoembolization)

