10.4.1 Analyses of Study Endpoints

For the primary endpoint, the proportion of CS patients who are at least somewhat satisfied with their overall symptom control at 6 months, a point estimate and the corresponding 95% CLs will be calculated. Secondarily, a point estimate and corresponding 95% CLs will be calculated for the proportion of CS patients who are very satisfied with their overall symptom control at 6 months. The 95% CLs will be unadjusted and based on the assumption of approximate normal distribution. Missing data will not be imputed in the main analysis of the primary endpoint. As a sensitivity analysis, a patient with a missing response at 6 months will be imputed as a non-responder. This approach corresponds to non-responder imputation.

In addition to the point estimates and 95% CLs for the primary endpoint, the frequency distribution of the categorical responses, on a 5-point Likert scale, to patient satisfaction with overall symptom control at 6 months will be presented. The patient satisfaction measure will also be summarized as an ordinal variable with a value of 1 corresponding to “very dissatisfied” up to 5 corresponding to “very satisfied”.

All the secondary endpoints correspond to proportions and will be summarized through point estimates and 95% CLs, as described above for the primary endpoint. Frequency distributions of the categorical responses and summary statistics of the corresponding ordinal values of the categories will be presented. The handling of patients with a response of “not applicable” to patient satisfaction with CS-related diarrhea control or patient satisfaction with CS-related flushing control in the analysis will be described in the SAP.

The 4 WPAI-SHP scores at Baseline and month 6 will be summarized, as well as the change from Baseline to month 6.

The incidences of at least 1 CS-related hospitalization, at least 1 CS-related ER visit, and mortality after Baseline will be calculated at each 6-month interval. Kaplan-Meier estimates of each time-to-event variable, including quartiles, medians, and their corresponding 95% CLs, will be presented. The association or relationship between the primary endpoint and each long-term health outcome will be evaluated through descriptive statistics and the use of statistical models, as appropriate. Any statistical models that will be used and the appropriateness and/or limitations of their use will be described in the SAP.

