2.3 Study Endpoints

2.3.1 *Primary Endpoint*

The primary endpoint of the study is the proportion of patients with CS who are satisfied with their overall symptom control, 6 months after initiating treatment with telotristat ethyl (XERMELO).

2.3.2 *Secondary Endpoints*

The following secondary endpoints will be assessed 6 months after initiating treatment with telotristat ethyl (XERMELO):

- The proportion of patients reporting satisfaction of CS-related diarrhea control
- The proportion of patients reporting satisfaction of CS-related flushing control
- The proportion of patients reporting reduction in rescue SSA use
- The proportion of patients reporting reduction in the dose of long-acting SSA injection
- The proportion of patients reporting reduction in the frequency of long-acting SSA injection
- The proportion of patients reporting an overall improvement in CS control after initiating XERMELO based on PGIC

- The proportions of patients who had reduction in work-related absenteeism, presenteeism, activity impairment, and overall productivity loss after initiating XERMELO based on the WPAI-SHP
- The proportion of patients reporting weight gain

2.3.3 *Other Endpoints*

Other endpoints include incidence of CS-related hospitalizations, incidence of CS-related emergency room (ER) visits, and incidence of mortality at 6-month intervals for up to 3 years after initiation of treatment with XERMELO.

Another endpoint, not described in the protocol, is the proportion of patients with a reduction in the number of bowel movements. This endpoint will be assessed at the 6-month Follow-up after initiation of treatment with XERMELO.

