3.2.3 Symptom Control

Satisfaction with control of diarrhea, flushing, and overall CS symptoms will be assessed at Baseline. Satisfaction with how XERMELO has controlled diarrhea, flushing, and overall CS symptoms will be assessed at the initial 6-month Follow-up only. The questionnaire items allow patients to choose a response on a 5-level Likert scale ranging from "Very dissatisfied" (level 1) to "Very satisfied" (level 5). For the assessments of satisfaction with control of diarrhea and flushing, "Not applicable" (level 0) is also 1 of the response options, for those patients who do not have the symptom that is being assessed.

At the initial 6-month Follow-up, patients will also be asked to assess the change in the number of bowel movements on a 7-level Likert scale from "A great deal worse" to "A great deal better." This assessment is not described in the study protocol.

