5 STATISTICAL ANALYSIS

5.1 Statistical Methods

5.1.1 General Considerations

Derivation of analytic variables will be detailed in a separate analytic variable specification document to be produced in Microsoft Excel. This document will be developed at the time of the first interim analysis and will be maintained through the final analysis. It will be provided to Lexicon at the end of the study, along with the corresponding SAS data sets.

All analyses will be descriptive in nature. For continuous and ordinal variables, the number of available observations, means, standard deviations (SDs), medians, minimums, and maximums will be provided. For categorical variables, the frequency and percentage in each category will be displayed. For computation of percentages, missing values and "Prefer not to answer" responses will not be included in the denominator. Results will be presented by study time point, where applicable. Additionally, all questionnaire data will be displayed in listings. Height and weight information will be collected in feet and inches and in pounds but will be summarized in the tables in centimeters and kilograms, respectively. By convention, dates will be displayed in DDMMYYYY format (eg, 17JAN2017). For the times since diagnosis of CS and diagnosis of primary NET and all time-to-event analyses, the date of Baseline questionnaire completion will be considered as Day 1, and times will be expressed in months or years, as appropriate. The day before the date of Baseline questionnaire completion will be considered Day -1; there will be no Day 0.

All analyses will be performed in SAS, Version 9.4 or higher (SAS Institute, Cary, NC).

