5.1.4 Primary and Secondary Endpoint Analyses

Responses to questionnaire items related to the primary and secondary endpoints will be summarized as categorical variables, as described in [Section 5.1.1](#). Items having ordinal response scales consisting of at least 5 categories will also be summarized as ordinal variables. Estimates of proportions for all primary and secondary endpoints at the initial 6-month Follow-up will be accompanied by 2-sided 95% CLs based on the normal distribution approximation.

For estimation of the proportions for the primary and secondary endpoints, patients will be categorized based on their responses to the corresponding questionnaire items as described in Table 1. Responses of "Not applicable" will be excluded from the denominator for computation of each proportion. Missing data will not be imputed, with the exception of a sensitivity analysis on the primary endpoint, whereby a patient with a missing response will be imputed as a non-responder (ie, neither "Very satisfied" nor "Somewhat satisfied"). Some endpoints will have supplemental/sensitivity analyses in addition to the main analysis, and specifications for those analyses are also shown in Table 1.

In addition to the proportions of patients reporting reduction from Baseline in the 4 domains of the WPAI-SHP, domain scores will be summarized at Baseline and at the initial 6-month Follow-up. The change in score for each domain over this 6-month interval will also be summarized as a continuous variable.

Table 1. Primary and Secondary Endpoint Definitions

	Definition for Main Analysis	Definition for Supplemental Analyses
Primary Endpoint (proportion of patients at 6 months after initiating treatment with XERMELO)		
Satisfaction with overall control of CS symptoms	“Very satisfied” or “Somewhat satisfied”	
 “Very satisfied” only [REDACTED]
Secondary Endpoints (proportions of patients at 6 months after initiating treatment with XERMELO)		
Satisfaction with control of CS-related diarrhea	“Very satisfied” or “Somewhat satisfied”	“Very satisfied” only
Satisfaction with control of CS-related flushing	“Very satisfied” or “Somewhat satisfied”	“Very satisfied” only
Reduction in rescue SSA use	“Less frequent”	N/A
Reduction in dose of long-acting SSAs	“Decreased”	N/A
Reduction in frequency of long-acting SSA injection	“Decreased”	N/A

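### Month-6 'Not applicable' answers leave the diarrhea and flushing satisfaction proportions whatever the Baseline answer, and no planned summary shows whether this moves the estimate (minor)

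*SAP*

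**What the plan says.** Protocol 10.4.1 defers the treatment of N/A on the two symptom items; for flushing it reads "patient satisfaction with CS-related flushing control in the analysis will be described in the SAP", and diarrhea is deferred in the same sentence. SAP 5.1.4 supplies the rule: N/A responses "will be excluded from the denominator for computation of each proportion". It does not refer to the Baseline answer.

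SAP 3.2.3 provides N/A (level 0) on the diarrhea and flushing items only, "for those patients who do not have the symptom that is being assessed". The three satisfaction items are asked at Baseline and again at month 6. On the second occasion the SAP says: "Satisfaction with how XERMELO has controlled diarrhea, flushing, and overall CS symptoms will be assessed at the initial 6-month Follow-up only". Protocol 5.1.1 lists the follow-up item as "Satisfaction with CS, CS-related diarrhea and/or flushing control after initiating XERMELO, where applicable", which may imply some routing.

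The diarrhea endpoint in SAP 2.3.2 is "The proportion of patients reporting satisfaction of CS-related diarrhea control"; the flushing endpoint is worded in parallel. In Table 1 the only supplemental definition for either endpoint is 'Very satisfied' only, and neither row is redacted. The one imputation analysis concerns missing answers on the primary endpoint (SAP 5.1.4 and 5.2).

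On output, SAP 5.1.1 says that for categorical variables "the frequency and percentage in each category will be displayed", and adds: "Results will be presented by study time point, where applicable. Additionally, all questionnaire data will be displayed in listings". It removes only missing and 'Prefer not to answer' responses from percentage denominators.

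**The concern.** Two kinds of patient can answer N/A at month 6. One did not have the symptom at Baseline either, and leaving that patient out is sensible. The other gave a satisfaction rating at Baseline and no longer has the symptom. Read literally, SAP 3.2.3 covers both, and SAP 5.1.4 removes both from numerator and denominator. The denominator then depends partly on a state reached after treatment began, and some of the patients removed may be those who did best.

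If that happens, the planned figure is lower than the proportion satisfied or symptom-free among patients who had the symptom at Baseline. That is a different quantity from reported satisfaction, but a reader could take the result that way, particularly for diarrhea, which is the drug's indication (Protocol 3.1). The bowel-movement item (SAP 5.1.5.2) partly covers improvement in diarrhea. Flushing has no comparable item.

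The planned tables do not separate the two groups. N/A totals at Baseline and at month 6 show the net change, not which patients moved from a rating to N/A.

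**Working it through.** **The plan's own figure.** SAP 2.4 gives 385 non-missing responses for the primary endpoint. Check: 1.96² × 0.5 × 0.5 / 0.05² = 384.2, rounded up to 385. With 40% dropout, 385 / 0.60 = 641.7, rounded up to 642 against the stated 643; the difference does not matter here. No size is stated for the diarrhea or flushing endpoints, so 385 month-6 responders serve below as an illustration.

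**Inputs, all assumed unless a source is given**
- p = the planned proportion among patients giving a level 1-5 rating at month 6. Assumed 60%, and the same whatever the Baseline answer.
- r = the share of Baseline-symptomatic month-6 responders (Baseline answer level 1-5) who answer N/A at month 6. The documents give no value; the range shown is 0 to 20%.
- Share of responders symptomatic at Baseline: 75% to 100%. Protocol 3.1 puts diarrhea at roughly 75% of patients with carcinoid syndrome in general. The share among patients starting XERMELO may be higher.

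**Formulas.** Among Baseline-symptomatic responders, a fraction 1 − r give a rating and a fraction p of those are satisfied.
- Satisfied or symptom no longer present: p(1 − r) + r. This exceeds the planned figure by r(1 − p).
- N/A counted as not satisfied: p(1 − r). This falls below the planned figure by rp.

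**Results at p = 60%**

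| r | Planned | N/A as satisfied or symptom no longer present | N/A as not satisfied (conservative bound) |
|---|---|---|---|
| 0% | 60.0% | 60.0% | 60.0% |
| 2% | 60.0% | 0.588 + 0.02 = 60.8% | 0.6 × 0.98 = 58.8% |
| 5% | 60.0% | 0.570 + 0.05 = 62.0% | 0.6 × 0.95 = 57.0% |
| 10% | 60.0% | 0.540 + 0.10 = 64.0% | 0.6 × 0.90 = 54.0% |
| 20% | 60.0% | 0.480 + 0.20 = 68.0% | 0.6 × 0.80 = 48.0% |

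**Scale.** The 95% half-width at 60% is 1.96 × √(0.24/385) = 4.9 points for a denominator of 385. For 289 (0.75 × 385 = 288.75, rounded up) it is 1.96 × √(0.24/289) = 5.6 points. The upward shift is 4.0 points at r = 10%, inside that half-width, and 8.0 points at r = 20%, outside it.

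**What the planned output shows.** Each item's frequency table may keep N/A in its denominator, because SAP 5.1.1 removes only missing and 'Prefer not to answer'. For example, with 77 N/A among 385 responders and 154 satisfied, the endpoint proportion is 154/308 = 50.0% and the frequency table would show 154/385 = 40.0%. A reader could see that N/A matters overall, but not how many of the 77 had rated the symptom at Baseline.

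**The case against.** The strongest reply is that the premise is unproven. The month-6 item asks how well XERMELO has controlled the symptom, and Protocol 5.1.1 makes participation depend on continued use. A patient still on the drug whose diarrhea has stopped has a natural answer, 'Very satisfied', and N/A can be read as saying that the symptom is not part of that patient's disease. This stands. The questionnaire wording and any routing are not visible, so r may be zero.

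Second, the rule fits the endpoint. Someone who answers N/A reports neither satisfaction nor dissatisfaction, and the SAP prespecified the handling as the protocol required. This also stands, and is why the main analysis should not change.

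Third, readers are not left without information. The listings pair each patient's Baseline and month-6 answers, so patients who moved to N/A can be found by hand. The primary item and the PGIC also cover overall symptom control, including in patients whose symptom resolved. This limits the point, but a listing is not a summary, and neither of those items gives the effect on the diarrhea or flushing proportion.

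Fourth, counting N/A as not satisfied sits badly with the SAP's own meaning of N/A. Agreed; that column is a conservative bound only.

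A reader might go further and infer that the rule hides treatment successes or biases the study's results. The documents do not support that: they give no frequency for N/A and do not show that resolved patients use it, and the primary endpoint is outside the rule.

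**Conclusion.** The point holds as a minor one. For two descriptive secondary endpoints in a single-arm study, every month-6 N/A answer is excluded without regard to Baseline. That can remove patients whose symptom resolved, and no planned summary isolates them or shows the effect on the estimate.

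The size cannot be found from the documents and may be nil. At an assumed planned proportion of 60% and r from 2% to 20%, the proportion satisfied or symptom-free among Baseline-symptomatic responders would be 0.8 to 8.0 points above the planned figure. With N/A counted as not satisfied it would be 1.2 to 12.0 points below. These figures rest on the assumed p and r, and on p not depending on the Baseline answer. They are illustrations, not predictions.

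**What to change.** Keep the SAP 5.1.4 rule as the main analysis, and make two additions for each symptom.

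1. A cross-tabulation of the Baseline response (N/A versus level 1-5) by the month-6 response, including N/A.
2. One supplemental entry in Table 1, restricted to patients with a Baseline answer of level 1-5 and a month-6 answer. Count month-6 N/A as 'satisfied or symptom no longer present', and show N/A as not satisfied as the conservative bound. Label the result as a different quantity from reported satisfaction.

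The cost is one small table and one Table 1 entry per symptom, with no new data collection. The drawbacks are slightly more output and some uncertainty in reading it, since some N/A answers may be errors or reflect other treatments. That is why this belongs in a supplemental analysis. If the cross-tabulation shows no movement from a rating to N/A, the question is closed.

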8.2.1.4 Work Productivity and Activity Impairment – Specific Health Problem (WPAI-SHP)

At Baseline and at month 6, patients will complete the WPAI-SHP questionnaire. The WPAI-SHP has 6 items and yields 4 types of scores: (1) Absenteeism (work time missed); (2) Presenteeism (impairment at work / reduced on-the-job effectiveness); (3) Work productivity loss (overall work impairment / absenteeism plus presenteeism); and, (4) Activity impairment. WPAI-SHP outcomes are expressed as impairment percentages, with higher numbers indicating greater impairment and less productivity (ie, worse outcomes).

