2.4 Sample Size Determination

The sample size was derived by satisfying design assumptions for the primary study endpoint of the proportion of patients with CS who are satisfied with their overall symptom control, 6 months after initiating treatment with telotristat ethyl (XERMELO). Of specific interest is the proportion of patients with CS who are at least somewhat satisfied with their control of CS at 6 months, defined as those patients with a response of either "very satisfied" or "somewhat satisfied". This proportion will be estimated as x/n , where x is the number of patients in the study who are either "Very satisfied" or "Somewhat satisfied", and n is the number of patients with a non-missing response for the primary endpoint. Two-sided 95% confidence limits (CLs) will be calculated for this proportion using normal approximation. The true proportion may be approximately 50%; hence, an expected proportion of 50% was used in the sample size calculation as it requires the largest n . It is desired for the proportion to be known with a precision, ω , of 5%, that is, for the CLs to be $(x/n) \pm \omega$. Based on the expected proportion of 50% and the precision requirement of 5%, $n = 385$ patients are needed to have a non-missing response for the primary endpoint. Assuming that 40% of the patients who participate in the study will drop out prior to the 6-month survey, then a minimum of $N = 643$ patients, with CS who initiate treatment with XERMELO, should be entered into the study.

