3.2.5 Work Productivity and Activity Impairment Questionnaire—Specific Health Problem (WPAI-SHP)

The WPAI-SHP is a self-administered questionnaire ([Reilly et al., 1993](#)) comprising 6 questions that measure the effect of health problems on participants' ability to work and participate in regular activities based on their experiences in the previous 7 days. This questionnaire will be administered at Baseline and at the initial 6-month Follow-up.

The WPAI-SHP includes 4 domains (absenteeism, presenteeism, work productivity loss, and activity impairment). All participants will be asked whether they are employed (Q1) and how their CS-related problems affected their regular activities (Q6). Employed participants will be asked about hours of work missed due to CS-related problems (Q2), hours of work missed for any reason (eg, vacation, holidays, time off to participate in this study) (Q3), hours actually worked (Q4), and the degree that CS affected their productivity while working (Q5). An integer scale from 0 to 10 is used for Q5 and Q6, where 0 corresponds to no effect and 10 corresponds to complete effect.

Responses to the items are scored to produce the following 4 domains:

- Absenteeism: work time missed due to CS = [REDACTED]
- Presenteeism: impairment while working due to CS = [REDACTED]

- Work productivity loss: overall work impairment due to CS = [REDACTED]
[REDACTED]
- Activity impairment: activity impairment due to CS = [REDACTED]

Each score is then multiplied by 100 to express domains in terms of impairment percentages, with higher numbers indicating greater impairment and less productivity (ie, worse outcomes).

3.2.6 *Carcinoid Syndrome-related Health Care Resource Utilization*

At Baseline and at each Follow-up, questionnaire items will ask patients about ER visits and hospitalizations during the prior 6-month period. Data collected will include the following:

- The number of ER visits and the CS-related reason for each visit
- The number of hospitalizations, the number of nights for each stay, and the CS-related reason for each hospitalization

3.2.7 *Study Discontinuation and Mortality*

Patients will be terminated from the study if they discontinue the use of XERMELO, withdraw consent for participation, or are lost to follow-up. Information on reasons for discontinuation will be provided by the specialty pharmacy.

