5.2 Missing Data

No imputations will be performed, except as noted for the sensitivity analysis for the primary endpoint as described in Table 1 ([Section 5.1.4](#)). In all other cases, missing data will be excluded and variables will be analyzed using the available observed data.

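### Patients who leave work by month 6 drop out of three of the four WPAI-SHP reduction proportions, and no sensitivity analysis shows the effect

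*SAP*

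**What the plan says.** - **Who answers what (SAP 3.2.5).** "All participants will be asked whether they are employed (Q1) and how their CS-related problems affected their regular activities (Q6"). The work items go to workers only: "Employed participants will be asked about hours of work missed due to CS-related problems (Q2"), and likewise the items on other missed hours, hours worked and impairment on the job (Q3 to Q5).
- **Direction of the scores (Protocol 8.2.1.4).** The scores are impairment percentages, "with higher numbers indicating greater impairment and less productivity (ie, worse outcomes"). On the 0 to 10 items in SAP 3.2.5, 0 means no effect.
- **Endpoint (SAP 5.1.4).** "In addition to the proportions of patients reporting reduction from Baseline in the 4 domains of the WPAI-SHP, domain scores will be summarized" at both time points, with the change as a continuous variable. The proportions "will be accompanied by 2-sided 95% CLs based on the normal distribution approximation".
- **Missing data (SAP 5.1.4 and 5.2).** The only imputation is a sensitivity analysis of the primary endpoint, in which a missing answer counts as non-response. Everywhere else, "missing data will be excluded and variables will be analyzed using the available observed data".
- **Table 1 (SAP 5.1.4).** The main definition of a reduction is blacked out for all four WPAI domains. The supplemental-analysis column is readable and shows N/A for all four. The scoring formulas in SAP 3.2.5 are also blacked out, and SAP 5.1.1 places variable derivations in a separate document.

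**The concern.** Take a patient who is employed at Baseline with some work impairment and is no longer employed at month 6. She completes the month-6 survey and answers Q1 in the negative, so Q2 to Q5 do not apply to her. She has no month-6 absenteeism, presenteeism or productivity-loss score and no change score. Under SAP 5.2 she is left out of the numerator and the denominator.

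This exclusion may be related to outcome. If she left work because of carcinoid syndrome, she is a patient whose working life did not improve, and removing her raises the reported proportion with a reduction. The primary endpoint has non-responder imputation as a check on this kind of loss; the work endpoints have nothing comparable. The continuous change score omits her too, and the separate Baseline and month-6 score summaries can describe different sets of workers.

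A second question arises for all four domains. A score of 0 cannot fall. The readable denominator rules remove only missing answers, refusals to answer and not-applicable responses. Whether a patient at 0 at Baseline counts as not reduced depends on the blacked-out definitions, so this can only be put as a question to the sponsor.

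**Working it through.** **Plan's own figure.** The SAP states no sample size or precision for the WPAI endpoints. Its only such figure is for the primary endpoint (SAP 2.4): expected proportion 50%, half-width 5%, two-sided 95% limits, 40% dropout.

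- n = z² × p(1 − p) / w² = 1.95996² × 0.25 / 0.05² = 384.15, rounded up to 385, as stated.
- N = 385 / (1 − 0.40) = 641.67, rounded up to 642. The SAP states 643; the difference of one patient is immaterial here.

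**Tracing the leaver through the text.**

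1. Not employed at month 6, so no answers to Q2 to Q5 (SAP 3.2.5).
2. No answers, so no month-6 score in the three work domains. Activity impairment comes from Q6, which everyone answers, so it is unaffected.
3. No score and no imputation, so excluded (SAP 5.1.4 and 5.2).
4. No supplemental analysis brings the patient back (Table 1, N/A).

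**Size of the leaver effect. All rates are assumptions.** Let s be the share of Baseline workers who answer the month-6 survey but no longer work, and r the share with a reduction among those still working.

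- Plan: r. Leavers counted as no reduction: r(1 − s). Gap: r × s.
- 100 Baseline workers, 10 leave, 40 of the other 90 improve: 40/90 = 44.4% against 40/100 = 40.0%, a gap of 4.4 points. If only 5 of the 10 exits are counted as failures, 40/95 = 42.1%.
- With r = 50% and s = 5%, 10% or 20%: 47.5%, 45.0% or 40.0% against 50.0%, a gap of 2.5, 5 or 10 points.

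**Against the sampling error.** If 20% to 50% of the 385 responders were employed at Baseline (assumed), that is about 77 to 192 patients. With 10% leaving, about 69 to 173 remain. At a proportion of 50%, the 95% half-width is 1.96 × √(0.25/69) = 11.8 points down to 1.96 × √(0.25/173) = 7.5 points. A 5-point shift lies inside those limits, but it is systematic and the limits do not reflect it.

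**Conditional point: Baseline score of 0.** This applies only if the blacked-out definitions do not already require a Baseline score above 0. Let f be the share of Baseline workers at 0. Take a 50% reduction rate among continuing workers above 0, s = 10%, and all leavers above 0 at Baseline.

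| Analysis | Formula | f = 30% | f = 60% |
|---|---|---|---|
| Zeros kept, leavers dropped | 0.5(0.9 − f)/0.9 | 33.3% | 16.7% |
| Baseline above 0, leavers dropped | by assumption | 50.0% | 50.0% |
| Baseline above 0, leavers as no reduction | 0.5(0.9 − f)/(1 − f) | 42.9% | 37.5% |

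For activity impairment no one is lost through employment. With zeros kept the figure would be 0.5(1 − f) = 35% or 20%, against 50% among those above 0.

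Dropping leavers raises the proportion and keeping zeros lowers it. The two depend on unrelated quantities, so they cannot be relied on to cancel.

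**The case against.** **The governing definitions are blacked out.** A reader might infer that the plan keeps Baseline-0 patients in the denominator. The documents do not support that as a fact: Table 1 decides it, its cells cannot be read, and blacked-out text is not missing from the plan. This part of the objection stands, and the point is therefore conditional. It does not rescue the leavers. A hidden requirement of employment at both times would drop them as well, and a hidden rule counting them as not reduced would conflict with the no-imputation statements in SAP 5.1.4 and 5.2.

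**Leaving work is not a WPAI outcome.** A reader might infer that the plan discards the instrument's worst outcome. That goes too far. The items listed in SAP 3.2.5 ask whether a patient is employed, not why work stopped, so retirement and exit because of carcinoid syndrome look alike. Counting all leavers as failures gives a pessimistic figure, suitable only for a sensitivity analysis.

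**Keeping zeros fits the objective.** SAP 2.2.2 and Protocol 4.2 ask for a proportion of patients, not of patients impaired at Baseline. Selecting on a positive score with 7-day recall also invites regression to the mean in a single-arm study. Both points are fair, so the restricted proportion belongs beside the all-patient one, not in its place.

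**Much will be visible anyway.** SAP 4.2 and 5.1.1 promise questionnaire summaries at each time point and full listings, so employment at Baseline and at month 6 should appear. But separate totals do not show who moved from work to no work, and a listing is not an analysis.

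**The endpoints are descriptive.** They are secondary, without a testing hierarchy, and Protocol 10.4 treats p-values as descriptive. This limits the weight of the point.

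**Conclusion.** On the readable text, patients employed at Baseline but not at month 6 are excluded from the reduction proportions for absenteeism, presenteeism and overall productivity loss, and no planned analysis shows the effect. If some of them left work because of carcinoid syndrome, those proportions are overstated. Under assumed exit rates of 5% to 20% and a 50% reduction rate, the most the exclusion could add is 2.5 to 10 points, reached if every leaver counts as a failure.

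Whether Baseline scores of 0 dilute any of the four proportions is open until the sponsor confirms the definitions. A reader might go further and infer that the reported figures would be driven mainly by job exits and zero scores rather than by change in impairment. The documents contain no WPAI rates, so that cannot be claimed.

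The primary endpoint is untouched. The change is worth making but lies between optional and recommended.

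**What to change.** In SAP 5.1.4 and Table 1:

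1. Cross-tabulate Q1 (employed yes or no) at Baseline by month 6, so that the numbers who stayed in, left and entered work are visible.
2. For the three work domains, add a sensitivity analysis that counts patients employed at Baseline and reporting no employment at month 6 as having no reduction. Describe it as a sensitivity analysis, because Q1 does not separate exit due to carcinoid syndrome from retirement. Patients with no month-6 survey are a separate question and should not be added here.
3. Confirm whether the definitions of a reduction are limited to Baseline scores above 0. If they are not, report each of the four proportions also among patients with a Baseline score above 0, next to the all-patient proportion.

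The cost is SAP wording and a few table rows. Q1 and the Baseline scores are already collected, and the main analysis does not change. The drawbacks are smaller denominators with wider limits in item 3, possible regression to the mean in that row, and some unrelated retirements counted as failures in item 2.
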